7.3. Lost to Follow Up

A participant will be considered lost to follow-up if they repeatedly fail to return for scheduled visits and are unable to be contacted by the study site. Site personnel or designee are expected to make diligent attempts to contact participants who fail to return for a scheduled visit or were otherwise unable to be followed up by the site.

8. Study Assessments and Procedures

Study procedures and their timing are summarized in the CWMM master protocol SoA (Section 1.3) and in the SoA of the relevant ISA.

Immediate safety concerns should be discussed with the sponsor immediately upon occurrence or awareness to determine if the participant should continue or discontinue study intervention.

Adherence to the CWMM and relevant study design elements, including those specified in the SoA and the inclusion and exclusion criteria, is essential and required for proper study execution.

All screening evaluations must be completed and reviewed to confirm that potential participants meet all eligibility criteria, including establishing eligibility for the CWMM master protocol and all currently available ISAs at the time of screening. Additionally, participant eligibility for a given ISA will be confirmed at the time of randomization to treatment within the ISA.

Unless otherwise specified in the relevant ISA, safety and efficacy assessments and sample collections should be completed prior to dosing at the dosing visits.

8.1. Efficacy Assessments

Efficacy-related assessments occur at visits specified in the CWMM master protocol SoA (Section 1.3) and in the relevant ISA.

Efficacy endpoints are described in this master protocol and the relevant ISA.

Primary

The primary efficacy measure is percent change body weight from baseline at the primary time point. Body weight measurements will be collected at specific clinic visits as summarized in the CWMM SoA (Section 1.3.1) and the SoA of the relevant ISA. Methods for measuring body weight are described in CWMM Section 10.8.

Secondary

The following secondary efficacy measure will be collected or calculated at the times shown in the CWMM SoA (Section 1.3.1) and the SoA of the relevant ISA:

- body weight, and
- BMI

Exploratory

CCI

- [REDACTED]
- [REDACTED]
- [REDACTED]
- [REDACTED]
- [REDACTED]
- [REDACTED]

8.1.1. Bioelectrical Impedance Analysis

A whole-body bioelectrical impedance analyzer will be used to assess endpoints related to body composition, as detailed in Section 10.13.

8.2. Safety Assessments

Visits and safety assessments

Safety assessments occur at visits specified in this master CWMM master protocol SoA (Section 1.3) and in the SoA of the relevant ISA.

Data collection and reporting

The AE data collection and reporting requirements are described in Section 8.3 and Section 10.3, Appendix 3.

For some interventions studied under this master protocol, there may be predefined adverse events of special interest (AESIs) or safety topics for monitoring beyond what is specified in this Master Protocol. If so, appropriate additional sample or data collections for AESIs or safety topics for monitoring will be specified in the ISAs.

Safety data monitoring

Each site's principal investigator will monitor safety data from their site throughout the study. Immediate safety concerns should be discussed with the sponsor immediately upon occurrence or awareness to determine if the participant should continue or discontinue study intervention.

Sponsor safety monitoring

The sponsor will monitor the safety data, including AEs and SAEs, discontinuations, vital signs, and clinical laboratory results by means of periodic blinded reviews and by other appropriate methods. The SAE reports will be reviewed in real time and across studies and will include review of applicable clinical safety and epidemiological publications from the literature. If this safety monitoring activity uncovers an issue that needs to be addressed by unblinding at the individual or group level, members of the IAC can conduct additional analyses of the safety data. The IAC is an advisory group for this study formed to protect the integrity of the study in unblinded safety data reviews. See Section 10.1, Appendix 1, Section 10.1.5.

Appropriateness of safety assessments

The safety assessments used in this study are routine elements of clinical health assessment and Phase 2 drug development.

Safety assessments described in this master protocol and in ISAs

The following sections describe safety assessments applicable to all ISAs.

See the ISAs for any additional safety assessments that may be applicable to a particular ISA.

8.2.1. Vital Signs

For each participant, vital sign measurements should be conducted according to the SoA (Section 1.3) and following the study-specific recommendations for performing these measurements included in Section 10.8.

Any clinically significant findings from vital sign measurement that result in a diagnosis and that occur after the participant receives the first dose of study intervention should be reported to Lilly or its designee as an AE via CRF.

8.2.2. Physical Examinations

For each participant, measurements including height and weight should be conducted according to the master protocol SoA and the ISA-specific SoA and following the study-specific recommendations for performing these measurements included in Section 10.8.

A complete physical examination will include, at a minimum, assessments of the

- skin, including feet
- cardiovascular system
- respiratory system
- GI system
- neurological system, and
- thyroid.

Investigators should pay special attention to clinical signs related to previous serious illnesses.

8.2.3. Electrocardiograms

Prior to collecting any blood samples, 12-lead ECGs will be collected for each participant as specified in the CWMM master protocol SoA (Section 1.3) and ISA SoA.

ECGs may also be collected at visits specified in the relevant ISA and at additional visits or time points when deemed clinically necessary.

- All V401 screening ECGs are to be collected locally.
- All digital single and triplicate ECGs, as applicable in an ISA, will be obtained using centrally provided ECG machines and will be electronically transmitted to a designated central ECG laboratory.
- 12-lead ECGs should be obtained after the participant has rested in a supine (or semi-supine) position for at least 10 minutes.

ECGs should be collected prior to collection of blood samples for laboratory testing, including PK samples.

For ECGs recorded in triplicate, consecutive replicate ECGs will be obtained at approximately 1-minute intervals and within 30 minutes prior to PK collection.

ECGs may be obtained at additional times, when deemed clinically necessary. Collection of more ECGs than expected at a particular time point is allowed when needed to ensure high-quality records.

ECGs will initially be interpreted by a qualified physician (the investigator or qualified designee) at the site as soon after the time of ECG collection as possible, and ideally while the participant is still present, to determine whether the participant meets entry criteria or for immediate participant management, should any clinically relevant findings be identified. Any clinically significant findings from ECGs that result in a diagnosis and that occur after the participant

receives the first dose of the investigational treatment should be reported in the CRF and to Lilly or its designee as an AE. The investigator (or qualified designee) must document their review of the ECG printed at the time of evaluation.

After enrollment, if a clinically significant increase in the QT/QTc interval from baseline or other clinically significant quantitative or qualitative change from baseline is identified by the investigator, the participant will be assessed by the investigator for symptoms (for example, palpitations, near syncope, or syncope) and to determine whether the participant can continue in the study. The investigator or qualified designee is responsible for determining if any change in participant management is needed and must document his/her review of the ECG printed at the time of evaluation from at least 1 of the replicate ECGs from each time point. The central ECG laboratory will perform a basic quality control check (for example, demographics and study details) of the digital ECG and then store the ECGs in a database. At a future time, the stored ECG data may be over-read by a cardiologist at the central ECG laboratory for further evaluation of machine-read measurements or to meet regulatory requirements.

ECGs will also be machine read for central evaluation of ECG parameters. The machine-read ECG intervals and HR may be used for data analyses and report-writing purposes, unless a cardiologist over-reading of the ECGs is conducted prior to completion of the final study report (in which case, the over-read data will be used).

8.2.4. Clinical Safety Laboratory Tests

Section 10.2 and the SoA (Section 1.3) lists the clinical laboratory tests to be performed during the screening period of this master protocol. See the relevant ISA for clinical laboratory tests to be performed during the study periods of an ISA.

All protocol-required laboratory assessments, as defined in the ISAs and in this master protocol, must be conducted in accordance with the SoAs, standard collection requirements, and the laboratory manuals.

Report the information as an AE if laboratory values from non-protocol-specified laboratory assessments performed at an investigator-designated local laboratory require a change in participant management or are considered clinically significant by the investigator, for example, SAE or AE or dose modification.

Reviewing and recording test results

The investigator must review the laboratory results, document this review, and report any clinically relevant changes occurring during the study as an AE. The laboratory results must be retained with source documents unless a Source Document Agreement or comparable document cites an electronic location that accommodates the expected retention duration. Clinically significant abnormal laboratory findings are those which are not associated with the underlying disease, unless judged by the investigator to be more severe than expected for the participant's condition.

Repeat testing after a clinically significant abnormal finding

All laboratory tests with values considered clinically significantly abnormal during participation in the study or after the last dose of study intervention should be repeated until the values return to normal or baseline or are no longer considered clinically significant by the investigator or Lilly-designated medical monitor.

If such values do not return to normal or baseline within a period of time judged reasonable by the investigator, the etiology should be identified and the sponsor notified.

8.2.5. Major Adverse Cardiovascular Events

Nonfatal and fatal cardiovascular AEs will be adjudicated by a committee of physicians external to Lilly with cardiology expertise. This committee will be blinded to treatment assignment. The nonfatal and fatal cardiovascular AEs to be adjudicated include

- myocardial infarction
- cerebrovascular events, including cerebrovascular accident (stroke) and transient ischemic attack deaths due to cardiovascular or unexplained causes
- hospitalization for unstable angina or heart failure, and
- coronary interventions, such as coronary artery bypass graft or percutaneous coronary intervention.

8.2.6. Deaths

All deaths will be adjudicated by a committee of physicians external to Lilly. This committee will be blinded to treatment assignment.

8.2.7. Hepatobiliary Disorders

All events of treatment-emergent biliary colic, cholecystitis, or other suspected events related to gallbladder disease should be evaluated and additional diagnostic tests performed, as needed. In cases of elevated liver laboratory tests, hepatic monitoring should be initiated as outlined in this CWMM master protocol.

8.2.8. Acute Renal Events

Renal safety will be assessed based on repeated renal functional assessment as well as assessment of AEs suggestive of acute renal failure or worsening of preexisting chronic renal failure.

8.2.9. Pregnancy Testing**Pregnancy testing at Visit 401**

Serum pregnancy testing will be performed using a central study laboratory during the screening period of this master protocol (Sections [1.3](#) and [10.2](#)).

Pregnancy testing after Visit 401

Urine pregnancy testing after Visit 401 will be performed locally according to the SoA of the relevant ISA if required. If a urine pregnancy test is not available, a serum pregnancy test performed by a local laboratory is an acceptable alternative.

If a urine pregnancy test is inconclusive at any visit, an additional serum pregnancy test should be performed. If the specified visit includes administration of study intervention, the pregnancy test must be “negative” within 24 hours before the study intervention is administered.

Pregnancy testing at any time during the study

Additional pregnancy testing may be performed at any time in the study, at the discretion of the investigator, if the participant’s menstrual period is missed or there is clinical suspicion of pregnancy, or as required by local law or regulation.

Discontinuation of participants who are pregnant

Participants who are pregnant will be permanently discontinued from the study intervention (Section 7.1).

8.2.10. Hepatic Safety Monitoring, Evaluation, and Criteria for Study Drug Interruption or Discontinuation

The following tables summarize actions to take based on abnormal hepatic laboratory or clinical changes.

Participants with normal or near normal baseline (ALT, AST, or ALP <1.5x ULN)

If this laboratory value is observed...	Then...		
	Initiate or continue close hepatic monitoring	Initiate comprehensive evaluation	Interrupt or discontinue study drug
ALT or AST ≥ 3 x ULN	X		
ALP ≥ 2 x ULN	X		
TBL ≥ 2 x ULN ^b	X		
ALT or AST ≥ 5 x ULN	X	X	
ALP ≥ 2.5 x ULN	X	X	
ALT or AST ≥ 3 x ULN with hepatic signs or symptoms ^a	X	X	X
ALT or AST ≥ 5 x ULN for more than 2 weeks	X	X	X
ALT or AST ≥ 8 x ULN	X	X	X
ALT or AST ≥ 3 x ULN and TBL ≥ 2 x ULN ^b or INR ≥ 1.5	X	X	X
ALP ≥ 3 x ULN	X	X	X
ALP ≥ 2.5 x ULN and TBL ≥ 2 x ULN ^b	X	X	X
ALP ≥ 2.5 x ULN with hepatic signs or symptoms ^a	X	X	X

^a Examples of hepatic signs or symptoms: severe fatigue, nausea, vomiting, right upper quadrant abdominal pain, fever, rash, and/or eosinophilia >5%.

^b In participants with Gilbert’s syndrome, the threshold for TBL may be higher.

Participants with elevated baseline (ALT, AST, or ALP ≥ 1.5 x ULN)

If this laboratory value is observed...	Then...		
	Initiate or continue close hepatic monitoring	Initiate comprehensive evaluation	Interrupt or discontinue study drug
ALT or AST ≥ 2 x baseline	X		
ALP ≥ 2 x baseline	X		
TBL ≥ 2 x ULN ^b	X		
ALT or AST ≥ 3 x baseline or ≥ 250 U/L (whichever occurs first)	X	X	
ALP ≥ 2.5 x baseline	X	X	
ALT or AST ≥ 2 x baseline or ≥ 250 U/L (whichever occurs first) with hepatic signs or symptoms ^a	X	X	X
ALT or AST ≥ 3 x baseline or ≥ 250 U/L (whichever occurs first) for more than 2 weeks	X	X	X
ALT or AST ≥ 4 x baseline or ≥ 400 U/L (whichever occurs first)	X	X	X
ALT or AST ≥ 2 x baseline or ≥ 250 U/L (whichever occurs first) and TBL ≥ 2 x ULN ^b or INR ≥ 1.5	X	X	X
ALP ≥ 3 x baseline	X	X	X
ALP ≥ 2.5 x baseline and TBL ≥ 2 x ULN ^b	X	X	X
ALP ≥ 2.5 x baseline with hepatic signs or symptoms ^a	X	X	X
If this laboratory value is observed...	Then...		
	Initiate or continue close hepatic monitoring	Initiate comprehensive evaluation	Interrupt or discontinue study drug
ALT or AST ≥ 2 x baseline	X		
ALP ≥ 2 x baseline	X		
TBL ≥ 2 x ULN ^b	X		
ALT or AST ≥ 3 x baseline or ≥ 250 U/L (whichever occurs first)	X	X	
ALP ≥ 2.5 x baseline	X	X	
ALT or AST ≥ 2 x baseline or ≥ 250 U/L (whichever occurs first) with hepatic signs or symptoms ^a	X	X	X
ALT or AST ≥ 3 x baseline or ≥ 250 U/L (whichever occurs first) for more than 2 weeks	X	X	X
ALT or AST ≥ 4 x baseline or ≥ 400 U/L (whichever occurs first)	X	X	X
ALT or AST ≥ 2 x baseline or ≥ 250 U/L (whichever occurs first) and TBL ≥ 2 x ULN ^b or INR ≥ 1.5	X	X	X
ALP ≥ 3 x baseline	X	X	X
ALP ≥ 2.5 x baseline and TBL ≥ 2 x ULN ^b	X	X	X
ALP ≥ 2.5 x baseline with hepatic signs or symptoms ^a	X	X	X

^a Examples of hepatic signs or symptoms: severe fatigue, nausea, vomiting, right upper quadrant abdominal pain, fever, rash, and/or eosinophilia >5%.

^b In participants with Gilbert's syndrome, the threshold for TBL may be higher.

8.2.10.1. Close Hepatic Monitoring

If a participant develops any 1 of these changes, initiate close hepatic monitoring:

Participants with normal or near normal baseline (ALT, AST, or ALP <1.5x ULN)	Participants with elevated baseline (ALT, AST, or ALP ≥1.5x ULN)
ALT or AST ≥3x ULN or	ALT or AST ≥2x baseline
ALP ≥2x ULN or	ALP ≥2x baseline
TBL ≥2x ULN ^a	TBL ≥2x ULN ^a

^a In participants with Gilbert's syndrome, the threshold for TBL may be higher.

Close hepatic monitoring should include these actions:

- Laboratory tests (Section 10.2), including ALT, AST, ALP, TBL, D. Bil, GGT, CK, and CBC with differential, should be checked within 48 to 72 hours of the detection of elevated liver tests to confirm the abnormality and to determine if it is increasing or decreasing.
- If the abnormality persists, clinical and laboratory monitoring should continue at a frequency of 2 to 3 times weekly until levels normalize or return to approximate baseline values.
- In addition to lab tests, basic evaluation for possible causes of abnormal liver tests should be initiated by the investigator in consultation with the Lilly-designated medical monitor. At a minimum, this evaluation should include physical examination and a thorough medical history, including current symptoms, recent illnesses (for example, heart failure, systemic infection, hypotension, or seizures), recent travel, concomitant medications (including over-the-counter), herbal and dietary supplements, history of alcohol drinking and other substance abuse.

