8.2.10.2. Comprehensive Hepatic Evaluation

If a participant develops any 1 of the following laboratory or clinical changes, initiate a comprehensive hepatic evaluation.

Participants with normal or near normal baseline (ALT, AST, or ALP <1.5x ULN)	Participants with elevated baseline (ALT, AST, or ALP ≥1.5x ULN)
ALT or AST ≥5x ULN or	ALT or AST ≥3x baseline or ≥250 U/L (whichever occurs first) or
ALP ≥2.5x ULN or	ALP ≥2.5x baseline or

ALT or AST ≥ 3 x ULN with hepatic signs or symptoms ^a or	ALT or AST ≥ 2 x baseline or ≥ 250 U/L (whichever occurs first) with hepatic signs or symptoms ^a or
ALT or AST ≥ 3 x ULN and TBL ≥ 2 x ULN ^b or INR ≥ 1.5	ALT or AST ≥ 2 x baseline or ≥ 250 U/L (whichever occurs first) and TBL ≥ 2 x ULN ^b or INR ≥ 1.5

a Examples of hepatic signs or symptoms: severe fatigue, nausea, vomiting, right upper quadrant abdominal pain, fever, rash, and/or eosinophilia $>5\%$.

b In participants with Gilbert's syndrome, the threshold for TBL may be higher.

Comprehensive hepatic evaluation should include these actions:

- At a minimum, comprehensive hepatic evaluation should include physical examination and a thorough medical history, as outlined above, as well as tests for PT-INR; tests for viral hepatitis A, B, C, and E; tests for autoimmune hepatitis; and an abdominal imaging study (for example, ultrasound or CT scan).
- Based on the participant's history and initial results, further testing should be considered in consultation with the Lilly-designated medical monitor, including tests for hepatitis D virus, cytomegalovirus, Epstein-Barr virus, acetaminophen levels, acetaminophen protein adducts, urine toxicology screen, Wilson's disease, blood alcohol levels, urinary ethyl glucuronide, and blood phosphatidylethanol.
- Based on the circumstances and the investigator's assessment of the participant's clinical condition, the investigator should consider referring the participant for a hepatologist or gastroenterologist consultation, and additional tests including magnetic resonance cholangiopancreatography, endoscopic retrograde cholangiopancreatography, cardiac echocardiogram, or a liver biopsy.
- Clinical and laboratory monitoring should continue at a frequency of 1 to 3 times weekly until levels normalize or return to approximate baseline values.
- All the medical information and tests results related to the hepatic monitoring and comprehensive hepatic evaluation should be collected and recorded in a hepatic safety CRF.

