8.2.10.3. Study Drug Interruption or Discontinuation

If a participant develops any 1 of the following laboratory or clinical changes, interrupt the study drug and continue close monitoring and comprehensive hepatic evaluation as described in Sections 8.2.10.1 and 8.2.10.2.

Participants with normal or near normal baseline (ALT, AST, or ALP <1.5x ULN) ALT or AST ≥ 3 x ULN with hepatic signs or symptoms ^a or ALT or AST ≥ 5 x ULN for more than 2 weeks or ALT or AST ≥ 8 x ULN or	Participants with elevated baseline (ALT, AST, or ALP ≥ 1.5x ULN) ALT or AST ≥ 2 x baseline or ≥ 250 U/L (whichever occurs first) with hepatic signs or symptoms ^a or ALT or AST ≥ 3 x baseline or ≥ 250 U/L (whichever occurs first) for more than 2 weeks or ALT or AST ≥ 4 x baseline or ≥ 400 U/L (whichever occurs first) or
---	---

ALT or AST ≥ 3 x ULN and TBL ≥ 2 x ULN^b or
 INR ≥ 1.5 **or**
 ALP ≥ 3 x ULN **or**
 ALP ≥ 2.5 x ULN and TBL ≥ 2 x ULN^b **or**
 ALP ≥ 2.5 x ULN with hepatic signs or
 symptoms^a

ALT or AST ≥ 2 x baseline or ≥ 250 U/L
 (whichever occurs first) and TBL ≥ 2 x ULN^b or INR ≥ 1.5 **or**
 ALP ≥ 3 x baseline **or**
 ALP ≥ 2.5 x baseline and TBL ≥ 2 x ULN^b **or**
 ALP ≥ 2.5 x baseline with hepatic signs or symptoms^a

^a Examples of hepatic signs or symptoms: severe fatigue, nausea, vomiting, right upper quadrant abdominal pain, fever, rash, and/or eosinophilia $>5\%$.

^b In participants with Gilbert's syndrome, the threshold for TBL may be higher.

Interruption or discontinuation of study drug should include these actions:

- While the participant is not receiving the study drug, clinical and laboratory monitoring should continue at a frequency of 1 to 3 times weekly until liver tests normalize or return to approximate baseline values.
- If the hepatic event continues past the anticipated end of the study (that is, data lock) the investigator should consult with the Lilly-designated medical monitor to determine the need for further data collection beyond the end date of the study (that is, data lock date).
- All the medical information and tests results related to the close hepatic monitoring and comprehensive hepatic evaluation should be collected and recorded in a hepatic safety CRF.

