10.2.1. Clinical Laboratory Tests

Clinical Laboratory Tests	Comments
Hematology	Assayed by Lilly-designated laboratory
Hemoglobin	
Hematocrit	
Erythrocyte count (RBCs – red blood cells)	
Mean cell volume	
Mean cell hemoglobin	
Mean cell hemoglobin concentration	
Leukocytes (WBCs – white blood cells)	

Platelets	
Differential	
Neutrophils	
Lymphocytes	
Monocytes	
Eosinophils	
Basophils	
Cell morphology (RBCs and WBCs) (performed only if clinically indicated)	
Clinical Chemistry	Assayed by Lilly-designated laboratory
Sodium	
Potassium	
Chloride	
Bicarbonate	
Total bilirubin (TBL)	
Direct bilirubin	
Alkaline phosphatase (ALP)	
Alanine aminotransferase (ALT)	
Aspartate aminotransferase (AST)	
Gamma-glutamyl transferase (GGT)	
Blood urea nitrogen (BUN)	
Creatinine	
Creatine kinase (CK)	
Uric acid	
Total protein	
Albumin	
Calcium	
Phosphorus	
Glucose	
Lipid Panel	Assayed by Lilly-designated laboratory
High-density lipoprotein (HDL)	
Low-density lipoprotein (LDL-C)	This value will be calculated. If triglycerides are >400 mg/dL, the direct LDL will be assayed
Very low-density lipoprotein (VLDL-C)	
Total cholesterol	
Triglycerides	
Urinalysis	Assayed by Lilly-designated laboratory
Specific gravity	
pH	
Protein	

Glucose	
Ketones	
Bilirubin	
Urobilinogen	
Blood	
Nitrite	
Urine leukocyte esterase	
Microscopic examination of sediment (performed only if clinically indicated)	
Hormones	Assayed by Lilly-designated laboratory
Thyroid-stimulating hormone (TSH)	
Hormones (females only)	
Serum pregnancy (beta-HCG)	
Follicle-stimulating hormone (FSH)	
Calculations	Generated by Lilly-designated Laboratory
Urinary albumin/creatinine ratio (UACR)	
EGFR CCI	
Serology	Assayed by Lilly-designated laboratory
HIV screening test	
Hepatitis B virus (HBV) testing:	
Hepatitis B surface antigen (HBsAg)	
Hepatitis B core antibody total (anti-HBc)	
HBV DNA	Performed only for participants who test negative for HBsAg and test positive for anti-HBc.
Hepatitis C virus (HCV) testing:	
HCV antibody	
HCV RNA	Performed only for participants who test positive for HCV antibodies.
Additional Testing	Assayed by Lilly-designated laboratory
Cystatin-C	
Calcitonin	
Pancreatic amylase	
Lipase	
HbA1c	Testing may be performed locally for Visit 601. All other visits assayed by Lilly-designated laboratory.

10.3. Appendix 3: Adverse Events and Serious Adverse Events: Definitions and Procedures for Recording, Evaluating, Follow-up, and Reporting

Information for ISAs having devices

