10.6. Appendix 6: Liver Safety: Suggested Actions and Follow-up Assessments

Hepatic evaluation testing

See CWMM master protocol Section 8.2.10 for guidance on appropriate test selection.

The Lilly-designated central laboratory should complete the analysis of all selected testing except for testing listed in the investigator-designated local laboratory table. The central laboratory will report results if a validated test or calculation is available.

Local testing may be performed *in addition to central testing* when necessary for immediate participant management.

The local laboratory must be qualified in accordance with applicable local regulations.

Tests assayed by Lilly-designated central laboratory	
Hepatic Hematology Panel	Hepatitis A virus (HAV) testing:
Hemoglobin	HAV total antibody
Hematocrit	HAV IgM antibody
Erythrocytes (RBCs - red blood cells)	Hepatitis B virus (HBV) testing:
Leukocytes (WBCs - white blood cells)	Hepatitis B surface antigen (HBsAg)
Differential:	Hepatitis B surface antibody (anti-HBs)
Neutrophils, segmented	Hepatitis B core total antibody (anti-HBc)
Lymphocytes	Hepatitis B core IgM antibody
Monocytes	HBV DNA ^b
Basophils	Hepatitis C virus (HCV) testing:
Eosinophils	HCV antibody
Platelets	HCV RNA ^b
Cell morphology (RBC and WBC)	Hepatitis D virus (HDV) testing:
Hepatic Clinical Chemistry Panel	HDV antibody
Total bilirubin	HDV IgM antibody
Direct bilirubin	Hepatitis E virus (HEV) testing:
Alkaline phosphatase (ALP)	HEV IgG antibody
Alanine aminotransferase (ALT)	HEV IgM antibody
Aspartate aminotransferase (AST)	HEV RNA ^b
Gamma-glutamyl transferase (GGT)	Anti-nuclear antibody (ANA)
Creatine kinase (CK)	Anti-smooth muscle antibody (ASMA)^a
Hepatic Coagulation Panel	Anti-actin antibody^c
Prothrombin time, INR (PT-INR)	Immunoglobulin IgA (quantitative)
Urine Chemistry	Immunoglobulin IgG (quantitative)
Drug screen	Immunoglobulin IgM (quantitative)
Haptoglobin	

Tests assayed ONLY by investigator-designated local laboratory	
Acetaminophen	Cytomegalovirus (CMV) testing:
Acetaminophen protein adducts	CMV antibody
Alkaline phosphatase isoenzymes	CMV DNA ^b
Ceruloplasmin	Herpes simplex virus (HSV) testing:
Copper	HSV (Type 1 and 2) antibody
Ethyl alcohol (EtOH)	HSV (Type 1 and 2) DNA ^b
Phosphatidylethanol (PEth)	Liver kidney microsomal type 1 (LKM-1) antibody
Urine Chemistry	Microbiology Culture:
Ethyl glucuronide (EtG)	Blood
Epstein-Barr virus (EBV) testing:	Urine
EBV antibody	
EBV DNA ^b	

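### INR ≥1.5 triggers comprehensive hepatic evaluation and drug interruption, but the master protocol requires no INR until that evaluation has begun, leaving one ALT/AST band where no required test supplies the value

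*Protocol*

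**What the plan says.** **Triggers.** The summary table in Section 8.2.10 for participants with normal or near-normal baseline contains the row "ALT or AST ≥ 3 x ULN and TBL ≥ 2 x ULN ^b or INR ≥ 1.5", marked for all three actions: close monitoring, comprehensive evaluation, and interruption or discontinuation. The elevated-baseline table has the matching row, with ALT/AST ≥2x baseline or ≥250 U/L. The lists in 8.2.10.2 and 8.2.10.3 repeat both. Section 8.2.10.3 is directive: "If a participant develops any 1 of the following laboratory or clinical changes, interrupt the study drug".

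**Tests at close monitoring (8.2.10.1).** "Laboratory tests (Section 10.2), including ALT, AST, ALP, TBL, D. Bil, GGT, CK, and CBC with differential, should be checked" within 48 to 72 hours. Clinical and laboratory monitoring then continues 2 to 3 times weekly if the abnormality persists. INR is not named.

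**Where INR is first required.** The minimum content of comprehensive evaluation in 8.2.10.2 is examination and history "as well as tests for PT-INR; tests for viral hepatitis A, B, C, and E", followed by further items.

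**Other places.** The laboratory list in 10.2.1 has no coagulation test. The standard ISA activities for the treatment period, post-treatment follow-up and early discontinuation (10.13.1 to 10.13.3) do not name INR. Appendix 6 (Section 10.6) lists PT-INR as a central-laboratory test, but on when to order it says: "See CWMM master protocol Section 8.2.10 for guidance on appropriate test selection".

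**The concern.** A trigger needs an input that exists when the trigger is read. Here INR is an entry criterion for the step in which it is first required. The other inputs to escalation are all available at close monitoring: TBL and ALP are in the panel, eosinophilia comes from the differential, and symptoms come from the history and examination. INR is the only criterion without a required source at that stage, which suggests an oversight.

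If so, a site can carry out every required step while a participant meets the Protocol's own interruption criterion unobserved and continues dosing. Section 8.2 presents these assessments as applying to all ISAs, so each ISA inherits the gap unless it closes it. Sites that order INR on their own initiative and sites that do not would apply the same rule differently. The elevated-baseline column is relevant in practice: exclusion criterion 23 admits ALT up to 3.0x ULN and exempts fatty liver disease.

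**Working it through.** The point involves no sample-size, power or alpha figure. The check is logical: in which combinations of findings is INR the only route left to an action, and is PT-INR already required there?

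**Reading of the rule.** The trigger is taken as ALT/AST ≥3x ULN and (TBL ≥2x ULN or INR ≥1.5).

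**Inputs, normal or near-normal baseline (8.2.10 to 8.2.10.3)**
- Comprehensive evaluation without INR: ALT/AST ≥5x ULN; or ALP ≥2.5x ULN; or ALT/AST ≥3x ULN with symptoms; or ALT/AST ≥3x ULN with TBL ≥2x ULN.
- Interruption without INR: ALT/AST ≥3x ULN with symptoms; or ≥5x ULN for more than 2 weeks; or ≥8x ULN; or ≥3x ULN with TBL ≥2x ULN; or ALP ≥3x ULN; or ALP ≥2.5x ULN with TBL ≥2x ULN or with symptoms.
- PT-INR is required only once comprehensive evaluation has been triggered.

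**Enumeration.** ALT/AST in four bands (<3, 3 to <5, 5 to <8, ≥8x ULN), ALP in four bands (<2, 2 to <2.5, 2.5 to <3, ≥3x ULN), TBL ≥2x ULN yes/no, symptoms yes/no, and duration over 2 weeks yes/no for the two upper ALT/AST bands only. That gives (2×1 + 2×2) × 4 × 2 × 2 = 96 combinations.

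**Result.** INR is the sole remaining route to interruption in 6 combinations, all with TBL <2x ULN, no symptoms and duration not over 2 weeks:

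| ALT/AST (x ULN) | ALP (x ULN) | Evaluation already triggered? | PT-INR required? |
|---|---|---|---|
| 3 to <5 | <2 | No | No |
| 3 to <5 | 2 to <2.5 | No | No |
| 3 to <5 | 2.5 to <3 | Yes (ALP) | Yes |
| 5 to <8 | <2 | Yes (ALT/AST) | Yes |
| 5 to <8 | 2 to <2.5 | Yes (ALT/AST) | Yes |
| 5 to <8 | 2.5 to <3 | Yes (both) | Yes |

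In the first two rows INR is also the sole remaining route to comprehensive evaluation. These are the only combinations where that is so, and PT-INR is required in neither. In the other 4 of the 6, PT-INR is already required and INR ≥1.5 can lead to interruption.

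**Elevated baseline.** The structure is the same by reading. With ALT/AST 2 to <3x baseline and <250 U/L, ALP <2.5x baseline, TBL <2x ULN and no symptoms, INR is the only route left and is not required. From ALT/AST ≥3x baseline or ≥250 U/L, comprehensive evaluation supplies PT-INR before the interruption threshold of 4x baseline or 400 U/L is reached.

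**The case against.** A reader might infer that the INR limb can never take effect. The text does not support that, for two reasons.

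- **INR before evaluation is optional, not excluded.** The close-monitoring list is introduced as inclusive rather than closed. Section 10.2 lets the investigator or medical monitor add tests whenever needed. Section 8.2.4 describes 10.2 as the screening list and leaves treatment-period tests to the ISAs, which are not shown and may schedule INR. Appendix 6 makes the test available centrally and allows local testing for immediate management. The summary tables act on an observed value whatever its source.
- **The interruption limb works higher up.** In 4 of the 6 combinations above, PT-INR is already required. The clearest case is ALT/AST 5 to <8x ULN for up to 2 weeks.

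Both points stand, and they narrow the finding. They do not remove it. The open list in 8.2.10.1 is tied to Section 10.2, which contains no INR. Appendix 6 sends test selection back to 8.2.10, where PT-INR appears only under comprehensive evaluation. The remaining routes are discretionary or depend on an ISA, whereas the rule that reads the value is directive.

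Two further inferences should not be drawn. One is that, without a data monitoring committee, this rule is the main protection. The Protocol also provides for sponsor safety review, site monitoring, a possible Internal Assessment Committee, repeated testing with medical-monitor consultation, and the investigator's authority to interrupt or stop drug. The other is that severe hepatic cases will be under-reported: the Protocol gives no figure for how often INR ≥1.5 occurs in the affected band.

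**Conclusion.** The point holds in limited form: the master protocol states a trigger whose input it does not assure when the trigger is to be applied. The gap affects INR as a trigger for comprehensive evaluation, and for interruption only in the lower ALT/AST band:

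- ALT/AST 3 to <5x ULN, ALP <2.5x ULN (normal or near-normal baseline); or
- ALT/AST 2 to <3x baseline and <250 U/L, ALP <2.5x baseline (elevated baseline);
- in both groups, TBL <2x ULN and no hepatic signs or symptoms.

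The number of participants affected cannot be estimated from the Protocol and is probably small. No endpoint, estimand or efficacy analysis is touched; the consequence is for individual safety and for consistent application across sites.

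The conclusion assumes that INR ≥1.5 counts only together with the ALT/AST threshold; if it were meant to stand alone, the group without a required INR would be larger. It also assumes that the relevant ISA does not itself require INR.

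**What to change.** Reconcile Sections 8.2.10, 8.2.10.1, 8.2.10.2, 8.2.10.3, 10.2.1 and Appendix 6 on when INR is obtained, so that the value the rule reads is available when the rule is applied. Leave every threshold unchanged. How the passages are brought into line is a clinical decision for the sponsor, and no monitoring rule is proposed here.

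The cost is a short text change and possibly one added laboratory test, already available centrally under Appendix 6, in the few participants under close hepatic monitoring.
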